#### **7.1.5.4.1 Survival Follow-up**

Once a subject experiences confirmed disease relapse/progression or starts a new anti-cancer therapy, the subject moves into the survival follow-up phase and should be contacted by telephone, if seen by an outside oncologist, every 3 month (12 weeks) for the first 2 years and then every 6 months (24 weeks) for the next 3 years to assess for survival status until death, withdrawal of consent, or at the end of the study, whichever occurs first.

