## **5.7 Subject Withdrawal/Discontinuation Criteria**

Subjects may withdraw consent at any time for any reason or be dropped from the trial at the discretion of the investigator should any untoward effect occur. In addition, a subject may be withdrawn by the investigator or the Sponsor if enrollment into the trial is inappropriate, the trial plan is violated, or for administrative and/or other safety reasons. Specific details regarding discontinuation or withdrawal are provided in Section 7.1.4 – Other Procedures.

A subject must be discontinued from the trial for any of the following reasons:

- The subject or legal representative (such as a parent or legal guardian) withdraws consent.
- Confirmed radiographic disease progression
- Unacceptable adverse experiences as described in Section 5.2.1.2

- Intercurrent illness that prevents further administration of treatment
- Investigator's decision to withdraw the subject
- The subject has a confirmed positive serum pregnancy test
- Noncompliance with trial treatment or procedure requirements
- The subject is lost to follow-up
- Administrative reasons

The End of Treatment and Follow-up visit procedures are listed in Section 6 (Protocol Flow Chart) and Section 7.1.5 (Visit Requirements). After the end of treatment, each subject will be followed for 30 days for adverse event monitoring (serious adverse events will be collected for 90 days after the end of treatment as described in Section 7.2.3.1). Subjects who discontinue for reasons other than progressive disease will have post-treatment follow-up for disease status until disease progression, initiating a non-study cancer treatment, withdrawing consent or becoming lost to follow-up. After documented disease progression each subject may be followed by telephone or in person for overall survival until death, withdrawal of consent, or the end of the study, whichever occurs first.

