### **5.8 Subject Replacement Strategy**

Patients who are unfit or unwilling to continue study after resection will be replaced. Patients who choose not to undergo surgical resection after initial dose of Pembrolizumab will be replaced. In addition, any patient who does not complete at least 1 week of adjuvant treatment will also be replaced.

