#### **7.1.1.5.3 Subsequent Anti-Cancer Therapy Status**

The investigator or qualified designee will review all new anti-neoplastic therapy initiated after the last dose of trial treatment. If a subject initiates a new anti-cancer therapy within 30 days after the last dose of trial treatment, the 30 day Safety Follow-up visit must occur before the first dose of the new therapy. Once new anti-cancer therapy has been initiated

the subject will move into survival follow-up.

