#### **7.1.2.6.3 Assessment of Disease**

Patients will be assessed for response 12 weeks after completion of radiation. A full physical exam including head and neck and fiberoptic exam should be performed if indicated per standard of care but not required per protocol every 12 weeks for first 2 years following CRT and then at least every 24 weeks for the next 3 years. For patients felt to have a relapse at any time, a thorough ENT exam as well as a repeat biopsy is recommended to confirm relapsed disease. Follow-up imaging in 4-8 weeks is also acceptable if biopsy is not yet felt to be necessary or is non-diagnostic. Patients will be followed clinically every three months and any concern for relapsed disease or progression should trigger either imaging or biopsy for confirmation. Patients will be followed for relapse for a total of 5 years.

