#### **7.1.5.4 Follow-up Visits**

Subjects will receive the follow-up PET/CT or CTs as outlined in flowchart in section 6.0. If subjects have no detectable relapse, they will complete the week 20 Safety Follow-up Visit (End of Treatment), and then they will move into the follow-up (post-treatment) stage of the study. Subjects will have follow-up visits every 3 months (12 weeks) either in person at a doctor visit or by phone (if being seen by outside oncologist) for the first 2 years and then every 6 months (24 weeks) for the next 3 years to monitor for relapse, or until time of

withdrawal of consent, or death, whichever comes first. Phone calls are an acceptable form of follow up for all subjects regardless if they are in the care of a local or outside oncologist. If subjects develop a relapse, they will continue to be followed at the time-points described in the flowchart in section 6.0. Every effort should be made to confirm relapse if suspected. During the follow up period, the follow up and survival follow up visits can be calculated in months rather than weeks in order to avoid potential protocol deviations with the scheduling window.

If patients have relapsed disease at time of post-treatment imaging, they should have follow-up imaging at discretion of investigator and, in addition to mandated 30-day safety follow-up, move into survival follow-up.

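### Relapse follow-up ends at non-study cancer treatment in some sections but not in others, while every dosed patient stays in the DFS analysis and no rule covers the unknown relapse status

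*Combined protocol and SAP*

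**What the plan says.** Three sections end or redirect relapse follow-up when other treatment starts.

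- Section 5.7 gives patients who discontinue for reasons other than progression "follow-up for disease status until disease progression, initiating a non-study cancer treatment, withdrawing consent or becoming lost to follow-up".
- Section 7.1.1.5.3 has the same trigger ("Once new anti-cancer therapy has been initiated") and sends the patient to survival follow-up.
- Section 7.1.5.4.1 says that once a patient "starts a new anti-cancer therapy, the subject moves into the survival follow-up phase", contacts are made "to assess for survival status until death, withdrawal of consent, or at the end of the study, whichever occurs first".

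Three sections make no such exception.

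- Section 2.1 plans assessment for DFS and OS every 3 months for 2 years, then every 6 months for 3 years.
- Section 7.1.2.6.3: "Patients will be followed for relapse for a total of 5 years".
- Section 7.1.5.4 monitors for relapse on the same schedule, to end at "withdrawal of consent, or death, whichever comes first".

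Sections 8.1.2 and 8.2.3.2 base efficacy on all patients with at least one pembrolizumab dose, grouped by post-resection stratum. Section 5.8 adds: "Patients who are unfit or unwilling to continue study after resection will be replaced". Replacement does not take the replaced patient out of that set.

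Section 8.2.2 counts any tumor or death from any cause as a DFS event; the summary definition in Section 8.1.2 counts relapse only. A censoring rule is given for OS and none for DFS. Section 8.2.4.2 analyses DFS by Kaplan-Meier and by a one-sample exact test at 1 year.

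**The concern.** Every patient receives pembrolizumab before surgery, so every patient enters the efficacy set before it is known whether they will take the adjuvant regimen. Section 5.8 expects some to be unfit or unwilling to go on after resection. Section 4.1.3 describes adjuvant radiation, with or without chemotherapy, as standard of care for this disease, so off-study adjuvant treatment is a plausible next step for some of them. On the Section 5.7 reading, collection of the primary endpoint stops there although the patient stays in the analysis.

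With no DFS rule, the analyst must either censor such patients in the Kaplan-Meier estimate or leave them out of the 1-year exact test. Section 8.1.3 makes the second easy, because it seeks 40 patients per stratum who have had a DFS event or at least one recurrence-free year. In both cases the result describes mainly those who stayed on the regimen. If leaving is related to prognosis, that differs from DFS in the dosed population. Because the sections conflict, sites may also collect different data.

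**Working it through.** **1. The plan's own figure (Section 8.1.3).** N = 40 per stratum, one-sided alpha 0.025, one-sample exact test. Take the smallest r with P(X ≥ r | 40, p0) ≤ 0.025.

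| Stratum | p0 | p1 | r | Exact alpha | Power |
|---|---|---|---|---|---|
| CRT | 65.4% | 86% | 33 | 0.0141 | 0.811 |
| RT | 68.8% | 88% | 34 | 0.0163 | 0.802 |

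The stated power of over 80% reproduces in both strata.

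**2. Effect of losing leavers.** Here a leaver is a dosed, resected patient who starts off-study cancer treatment without a recorded relapse. The documents give neither the share of leavers, f, nor their 1-year DFS, d; both are assumptions. Suppose that the whole dosed stratum is at the null rate p0 and leavers are lost from about time zero. The rate among the rest is then

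p_rest = (p0 − f·d) / (1 − f),

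and the type I error becomes P(X ≥ r | 40, p_rest).

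Example, CRT, f = 0.10, d = 0.50: (0.654 − 0.050)/0.90 = 0.671, which is 1.7 points above the null, and the type I error is 0.024.

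| f | d | CRT p_rest | CRT type I error | RT p_rest | RT type I error |
|---|---|---|---|---|---|
| 0 | – | 0.654 | 0.014 | 0.688 | 0.016 |
| 0.10 | 0.20 | 0.704 | 0.062 | 0.742 | 0.079 |
| 0.10 | 0.50 | 0.671 | 0.024 | 0.709 | 0.031 |
| 0.10 | 0.80 | 0.638 | 0.008 | 0.676 | 0.011 |
| 0.10 | 0.90 | 0.627 | 0.006 | 0.664 | 0.007 |

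At f = 0.10 the null rate is overstated by 1.7 to 5.4 points if d is 20-50%, and understated by 1.2 to 2.7 points if d is 80-90%. At f = 0.05 and d = 20-50%, the type I error is 1.8-3.6%.

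**3. Bounds that need no assumed leaver DFS.** Take a just-significant result in 40 evaluable patients and add four dosed, replaced leavers of unknown status, so n = 44.

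- CRT, 33/40 (p = 0.014): 33/44 if all four failed gives p = 0.117; 37/44 if none failed gives p = 0.005.
- RT, 34/40 (p = 0.016): 34/44 gives p = 0.146; 38/44 gives p = 0.006.

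The critical counts at n = 44 are 36 (CRT) and 37 (RT). Significance therefore survives only if at least three of the four were disease-free at 1 year.

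**The case against.** A reader might infer that the plan censors these patients informatively and so overstates DFS. The documents do not support that, for four reasons.

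- **No censoring rule is stated.** There is none for DFS, so censoring is an inference about what an analyst would do. Sections 2.1, 7.1.2.6.3 and 7.1.5.4 can be read as requiring relapse data throughout. This stands: the defect is a conflict plus a missing rule, not a wrong rule. The sections tied to new therapy are, however, the more specific ones, and a site could reasonably follow them.
- **Not every leaver triggers the rule.** Patients unfit for adjuvant treatment may receive none, and Section 5.7 then keeps them in disease-status follow-up. The prohibited list in Section 5.4.2 includes live vaccines and steroids, which are not cancer treatment. Neither new anti-cancer therapy nor non-study cancer treatment is defined, so it is unclear whether standard radiation or cisplatin given off study counts. No figure shows how common this would be.
- **The direction is not established.** The upward bias in step 2 comes from assuming leaver DFS of 20-50%, below the null. Unwilling patients need not have a worse prognosis, and Section 5.3 allows withdrawal of patients with low-risk pathology. In reply, those low-risk patients are less likely to start new cancer treatment, so upward bias may be the likelier case, but the documents do not settle it.
- **Deaths are still collected.** Survival status is sought after new therapy, and Section 8.2.2 counts deaths as DFS events. The loss is mainly of relapses, and step 2 is an upper bound. Under the relapse-only definition in Section 8.1.2 this mitigation disappears.

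**Conclusion.** The point holds as an inconsistency that can lose primary-endpoint data. Sections 5.7, 7.1.1.5.3 and 7.1.5.4.1 stop relapse follow-up at non-study cancer treatment, most explicitly in 5.7. That conflicts with Sections 2.1, 7.1.2.6.3 and 7.1.5.4 and with an efficacy set of all dosed patients. The resulting bias in DFS is upward if leavers do worse than the rest and downward if they do better.

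The size depends on a leaver share and a leaver DFS that the documents do not give. The step 2 figures are illustrative limits in both directions. The step 3 bounds need only an assumed number of leavers, and show that four patients of unknown status can decide a borderline result. The planned sample size and power are unaffected. The priority is low, but the correction is cheap.

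**What to change.** 1. Reconcile Sections 5.7, 7.1.1.5.3 and 7.1.5.4.1 with Sections 2.1, 7.1.2.6.3 and 7.1.5.4, so that relapse status is collected for every dosed patient at the 3- and 6-monthly contacts already scheduled, until relapse, death, withdrawal of consent or end of study, regardless of new therapy.
2. State in Section 8.2.2 that DFS is not censored at the start of new therapy, and align the DFS definition in Section 8.1.2 with it.
3. State how a patient with unknown 1-year status enters the exact test, and add a best-case/worst-case sensitivity analysis like step 3.

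The cost is one extra item at contacts already planned, with no change to treatment or sample size. Patients who withdraw consent cannot be recovered this way; the sensitivity analysis covers them.

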### **7.2 Assessing and Recording Adverse Events**

An adverse event is defined as any untoward medical occurrence in a patient or clinical investigation subject administered a pharmaceutical product and which does not necessarily have to have a causal relationship with this treatment. An adverse event can therefore be any unfavorable and unintended sign (including an abnormal laboratory finding, for example), symptom, or disease temporally associated with the use of a medicinal product or protocol-specified procedure, whether or not considered related to the medicinal product or protocol-specified procedure. Any worsening (i.e., any clinically significant adverse change in frequency and/or intensity) of a preexisting condition that is temporally associated with the use of Merck's product, is also an adverse event.

Changes resulting from normal growth and development that do not vary significantly in frequency or severity from expected levels are not to be considered adverse events. Examples of this may include, but are not limited to, teething, typical crying in infants and children and onset of menses or menopause occurring at a physiologically appropriate time.

Merck product includes any pharmaceutical product, biological product, device, diagnostic agent or protocol-specified procedure, whether investigational (including placebo or active comparator medication) or marketed, manufactured by, licensed by, provided by or distributed by Merck for human use.

Adverse events may occur during the course of the use of Merck product in clinical trials or within the follow-up period specified by the protocol, or prescribed in clinical practice, from overdose (whether accidental or intentional), from abuse and from withdrawal.

Adverse events may also occur in screened subjects during any pre-allocation baseline period as a result of a protocol-specified intervention, including washout or discontinuation of usual therapy, diet, placebo treatment or a procedure.

Progression of the cancer under study is not considered an adverse event unless it is considered to be drug related by the investigator.

All adverse events will be recorded from the time the consent form is signed through 30 days following cessation of treatment and at each examination on the Adverse Event case report forms/worksheets. The reporting timeframe for adverse events meeting any serious criteria is described in section 7.2.3.1.

If any adverse events related to study drug, pembrolizumab continue after the 30 days post treatment, they should be followed until resolution and/or if they are ongoing at the end of the follow up period, they should continue to be followed per standard of care per their MD.

New SAE/AE's are to be collected and documented in the study EDC during follow up (past 30 days following cessation of treatment) only if they are found to be related to study drug, pembrolizumab.

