#### **5.2.2.2 Pembrolizumab Guidelines**

Pembrolizumab 200 mg will be administered as a 30 minute IV infusion every 3 weeks. Infuse pembrolizumab (MK-3475) over approximately 30 minutes, with a window of -5 and +10 minutes, through a peripheral line or indwelling catheter. The first dose will be given no more than 3 weeks and no less than 7 days prior to resection. Ideally, the pre-surgery dose of Pembrolizumab will be given between 1-2 weeks before surgery. Post-surgery, Pembrolizumab will be between 4 and 11 weeks and will continue during radiation and 3 months after completion. The first adjuvant Pembrolizumab dose is to begin 1 week prior to radiation.

Pembrolizumab will be administered before Cisplatin on days they are given together. If fluids are administered along with Pembrolizumab, then hydration should include only NS. Radiation may be given before or after infusions. If a Pembrolizumab dose is missed outside the +/-1 day window up to week 7 and +/-3 day window week 10 and beyond per the schedule of events, it should be skipped and not made up.

The Pharmacy Manual contains specific instructions for the preparation of the Pembrolizumab infusion fluid and administration of infusion solution.

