## **6.0 TRIAL FLOW CHART**

### **6.1 Study Flow Chart**

Trial Period:	Screening Phase		Pre-surgery Dose	Surgery	Adjuvant Treatment										End of Treatment	Post-Treatment		
	Pre-screening (Visit 1)	Main Study Screening (Visit 2) P			1	2	3	4	5	6	7	8	9	10	NA	Safety Follow-up n	Survival Follow-Up a	
Treatment Dose Title:			Pre-Surgery Dose P		28 to 77	± 1	± 1	± 1	± 1	± 1	± 1	± 3	± 3	± 3	± 14	Discon		
Scheduling Window (Days):	-35 to -7	-22 to -7	-21 to -7	0												At time of Discon c	30 days and 3 months post discon	+/- 2 weeks
Adjuvant Treatment (Week):					1	2	3	4	5	6	7	10	13	16	19	(20 d )	20 d	
Administrative Procedures																		
Informed Consent	X	X o	X o															
Inclusion/Exclusion Criteria		X																
Demographics and Medical History		X																
Prior and Concomitant Medication Review		X	X		X	X	X	X	X	X	X	X	X	X	X	X	X	X
Pembrolizumab Administration j			X		X		X		X		X	X	X	X				
Cisplatin 40mg/m  weekly if indicated b					X	X	X	X	X	X	X							
Radiation 2-2.2 Gy Fxs M-F					X	X	X	X	X	X	X							

Trial Period:	Screening Phase		Pre-surgery Dose	Surgery	Adjuvant Treatment										End of Treatment	Post-Treatment		
	Pre-screening (Visit 1)	Main Study Screening (Visit 2) P			1	2	3	4	5	6	7	8	9	10	NA	Safety Follow-up n	Survival Follow-Up a	
Treatment Dose Title:			Pre-Surgery Dose P													Discon		
Scheduling Window (Days):	-35 to -7	-22 to -7	-21 to -7	0	28 to 77	± 1	± 1	± 1	± 1	± 1	± 1	± 3	± 3	± 3	± 14	At time of Discon c	30 days and 3 months post discon	+/- 2 weeks
Adjuvant Treatment (Week):					1	2	3	4	5	6	7	10	13	16	19	(20 d )	20 d	
Post-study anticancer therapy status																X		X
Survival Status																X	X	X
Clinical Procedures/Assessments																		
Review Adverse Events		X	X	X	X	X	X	X	X	X	X	X	X	X	X	X	X	
Full Physical Examination e		X														X	X	
Directed Physical Examination					X			X			X	X	X	X			X	
Dental Exam		X h																
Dysphagia/Swallowing Function					X i													
Vital Signs and Weight		X	X		X	X	X	X	X	X	X	X	X	X	X	X	X	

Trial Period:	Screening Phase		Pre-surgery Dose	Surgery	Adjuvant Treatment										End of Treatment	Post-Treatment		

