## **8.0 STATISTICAL ANALYSIS PLAN**

### **8.1 Statistical Analysis Plan Summary**

#### **8.1.1 Safety Analysis**

The All-Patients-as-Treated (APaT) population will be employed for safety analyses. The safety endpoints are all adverse events graded from 1 to 5. Fisher's exact test will be used to compare the proportion of adverse events among patients treated by Pembrolizumab + radiotherapy in this study with historical patients treated by radiotherapy only and compare patients treated by Pembrolizumab + radiotherapy + Cisplatin in this study with historical patients treated by radiotherapy + Cisplatin. Both the adverse events by grade as well as severe adverse event (SAE; yes/no) will be analyzed. RTOG 9501 data will be used for historical controls using targeted rates of 50% for CRT and 39% for RT. We expect that the addition of Pembrolizumab will not add undue toxicity over standard treatment and therefore, will give insight to the development of future trials.

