## 8.2 Statistical Analysis Plan

### 8.2.1 Safety Endpoints

The safety endpoints are all adverse events graded from 1 to 5 described in Section 7.

The Lead-in population will be assessed for DLTs as described in section 5.2.2.3.1.

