### 8.2.3 Analysis Population

### **8.2.3.1 Safety Analysis Population**

The All Patients as Treated (APaT) population will be used for the analysis of safety data in this study. The APaT population consists of all subjects who received at least 1 dose of study treatment. Only those patients who continue treatment after resection will be compared to RTOG 9501 historical controls. Those who receive only pre-resection Pembrolizumab will still be analyzed for safety but there will be no direct comparison. Subjects will be included in the treatment group corresponding to the trial treatment they actually received for the analysis of safety data. Subjects who take incorrect trial treatment for the entire treatment period will be included in the treatment group corresponding to the trial treatment actually received. At least one laboratory or vital sign measurement obtained subsequent to at least one dose of trial treatment is required for inclusion in the analysis of each specific parameter. To assess change from baseline, a baseline measurement is also required.

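### The RTOG 9501 toxicity comparison sets no start date for events, so as written it counts peri-operative events against rates from an adjuvant trial

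*Combined protocol and SAP*

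**What the plan says.** - **Recording window (7.2).** "All adverse events will be recorded from the time the consent form is signed through 30 days following cessation of treatment". An adverse event counts "whether or not considered related to the medicinal product or protocol-specified procedure".
- **Collection (6.1).** The flow chart row "Review Adverse Events" is marked at screening, at the pre-surgery dose, at surgery and at every adjuvant visit.
- **Endpoint (8.2.1).** "The safety endpoints are all adverse events graded from 1 to 5 described in Section 7". Section 8.1.1 likewise takes all graded events.
- **Comparison (8.1.1, 8.2.4.1).** Each treatment group is tested against an RTOG 9501 rate of grade 3 and 4 events: 50% for CRT and 39% for RT. Section 8.1.1 names Fisher's exact test, and 8.2.4.1 says only that an exact test will be used. Neither gives a significance level or a start date for the events.
- **Who is compared (8.2.3.1).** "Only those patients who continue treatment after resection will be compared to RTOG 9501 historical controls". Patients who had only the pre-resection dose are described without a comparison.
- **Comparator (4.2.3.2).** RTOG 9501 is described as an adjuvant study, entered on extracapsular extension, positive margins or at least two involved nodes.
- **Timing (5.2.2.2, Pembrolizumab Guidelines).** "The first dose will be given no more than 3 weeks and no less than 7 days prior to resection". "Post-surgery, Pembrolizumab will be between 4 and 11 weeks".

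**The concern.** The plan recognises that pre-resection exposure has no counterpart in RTOG 9501, because it leaves patients who stop at that stage out of the comparison. It does not do the same for events. Take a patient with a grade 3 wound complication who recovers and starts adjuvant treatment. That patient is compared, and nothing in the plan removes the event.

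Toxicity is the first primary objective (3.1), and 8.1.1 states the expectation that pembrolizumab adds no undue toxicity. A peri-operative event in the trial's rate, with none in the historical rate, would work against that expectation for a reason unrelated to the regimen. If the window is left open, it could also be chosen after the rates are known.

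**Working it through.** **No figure to reproduce.** The safety comparison has no stated power, threshold or sample size. The plan's only power statement is for 1-year DFS (8.1.3: exact one-sample test, one-sided 0.025, N=40). It reproduces at 81.1% (65.4% against 86%, at least 33/40) and 80.2% (68.8% against 88%, at least 34/40). That test and level are borrowed below for illustration.

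**Length of the unmatched period.** From first pembrolizumab dose to first adjuvant dose:
- shortest: 7 + 28 = 35 days
- longest: 21 + 77 = 98 days

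Time from consent to the first dose comes on top.

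**Direction.** A patient counts once if any grade 3-4 event falls in the window. Opening the window earlier can add such patients but cannot remove any.

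**Size, under assumptions.** Let p0 be the RTOG 9501 rate. Let s be the share of continuing patients, otherwise free of grade 3-4 events, who have one before adjuvant treatment. With no true excess in the adjuvant phase, the apparent rate is

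p = p0 + (1 − p0) × s

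The cut-off is the smallest r with P(X ≥ r | 40, p0) ≤ 0.025. This gives 27/40 for CRT (size 1.9%) and 23/40 for RT (size 1.4%). The chance of a false excess is P(X ≥ r | 40, p).

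| s (assumed) | CRT apparent rate | CRT false excess | RT apparent rate | RT false excess |
|---|---|---|---|---|
| 0 | 50.0% | 1.9% | 39.0% | 1.4% |
| 2% | 51.0% | 2.6% | 40.2% | 2.0% |
| 5% | 52.5% | 4.0% | 42.1% | 3.5% |
| 10% | 55.0% | 7.5% | 45.1% | 7.9% |
| 15% | 57.5% | 13.1% | 48.2% | 15.3% |

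**Dependence on the test.** Suppose instead Fisher's test, two-sided at 0.05, against an assumed historical table of 100 to 200 patients.
- CRT, historical rate exactly 50%: the cut-off is 28/40. The false-excess probability is P(X ≥ 28 | 40, 0.50) = 0.8% at s = 0 and 3.9-7.3% at s = 10-15%.
- RT, historical table 58/150 or 78/200: the cut-off stays at 23, so the column above is unchanged.
- RT, historical table 39/100: the cut-off is 24, and s = 10-15% gives 4.2-9.0%.

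**The case against.** **Section 7.2 is a rule for case report forms.** Sections 8.1.1 and 8.2.4.1 set no analysis window, the groups are named by adjuvant treatment, and 8.2.3.1 suggests that the authors had the adjuvant phase in mind. An analyst might count adjuvant events only. This is a fair reading of intent, but 8.2.1 defines the endpoint by reference to Section 7 and nothing narrows it. The text as it stands includes the earlier events.

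**The historical window is unknown.** A reader might infer that the 50% and 39% rates certainly contain no surgical period. The documents support post-operative entry, but give neither the start nor the end of RTOG 9501's event collection. The inference is reasonable and should be labelled as one.

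**The size is not established.** A reader might also infer that surgical complications will inflate the result by a known amount. The documents give no surgical event rate and no significance level for safety. Section 5.8 replaces patients unfit to continue after resection and 8.2.3.1 leaves them out of the comparison, so the worst peri-operative courses tend to drop out. That lowers s without making it zero.

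**No action hangs on this comparison.** It would be wrong to infer that peri-operative events could stop the trial through it. The numerical stopping rule is the lead-in rule (5.2.2.3), which counts only events the investigator attributes to pembrolizumab (5.2.2.3.1). What is affected is the reported conclusion on toxicity.

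**A later start has its own bias.** The pre-surgical dose is experimental treatment, and 5.2.2.4.1 notes that immune events may follow shortly after the first dose. Counting only from adjuvant treatment drops such events and favours the regimen. This objection stands, and the fix has to answer it.

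**Conclusion.** The plan restricts the patients compared with RTOG 9501 but not their events. As written, peri-operative grade 3-4 events in continuing patients are counted against rates from an adjuvant trial. Any resulting bias raises the apparent toxicity, and no other section corrects it.

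Its size cannot be read from the documents. The illustrative rise, from 1.9% to 2.6-13% (CRT) and from 1.4% to 2.0-15% (RT), rests on:
- an assumed s of 2-15%;
- no true excess in the adjuvant phase;
- n = 40 per stratum;
- a one-sample exact test at a level taken from the DFS analysis;
- historical rates that exclude the surgical period.

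At the low end the effect is minor. The case for acting is that the window is undefined in a primary safety comparison and can be settled cheaply before analysis.

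**What to change.** - In 8.1.1 and 8.2.4.1, state that the RTOG 9501 comparison counts grade 3-4 events with onset or worsening on or after the first adjuvant treatment.
- Tabulate events from consent to that point separately, covering the pre-surgical and peri-operative periods.
- Add a sensitivity comparison that also counts pre-adjuvant events attributed to pembrolizumab.
- Name the test and its level in both sections.

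The cost is a few sentences and one extra table. Section 7.2.4 (Table 6 and the text before it) already requires start and stop dates, every change of grade and a causality assessment, so no new data are needed.

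The downside is that the main comparison leaves out toxicity from the pre-surgical dose. The separate table and the sensitivity analysis keep it visible. The end of the window also stays unmatched, because pembrolizumab continues for 3 months after radiation and events are recorded for 30 days more. If RTOG 9501's collection period can be obtained, the SAP should state it.
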